#### ***Condition under which a report is not required***

Please note that the non-reporting of any event, for one of the reasons listed below to the relevant Competent Authority, does not exclude the obligation of communicating them by the user to the manufacturer, immediately and without any delay that cannot be justified.

The communication to EMOLED S.r.l. can be done by any means (telephone / fax / e-mail) to the channels listed in the User Manual supplied with the Device. Furthermore, in order to encourage and facilitate any report to the manufacturer, for the devices that they markets, in the User Manual supplied to the user together with the medical device, there is a Reporting Form to be filled in to the Manufacturer for any report from the users.

Here are some of the conditions that may not require reporting:

- Inadequacy of a device found by the user before use: all deficiencies of the device detected (and which could not be identified) by the user before use of the device itself, must not be reported.
- Event caused by the patient's condition: when the manufacturer becomes aware that the main cause of the event is related to the patient's condition, the event does not require reporting. These conditions may pre-exist or occur during the use of the device. To justify the non-reporting, the manufacturer must have information demonstrating that the device was functioning in accordance with the established performance and therefore could not have caused or contributed to death or serious deterioration in health. This conclusion must be shared by a person qualified to make a medical judgment. The manufacturer is recommended to involve a clinician in this decision.
- Exceeding the deadline or expiration date of the device: when the only cause of the event was the exceeding of the expiry date of the device, as indicated by the manufacturer, and the failure modes are not unusual, the incident must not be reported.
- Correct operation of the protection system against a fault: events that have not led to serious deterioration of the state of health or death must not be reported, as a design feature has prevented a fault from constituting a danger (in compliance with the appropriate standards or to the documented design inputs). EMOLED S.r.l. establishes, implements and documents a Risk Management System, at the same time as the company Quality Management System, for the devices it markets in accordance with the current, cogent and collateral legislation applicable to it. It defines and maintains updated a risk analysis of the EMOLED Device v.1 (Code 9800010001), including its SanaLight Software in version 2.1 as defined in the reference risk analysis document

for that product / product family in its latest review (9800010001\_RAN - Risk Analysis) provided by the manufacturer together with the rest of the documentation given to the investigator.

As concerns the risks associated with the use, according to what has emerged and reported in the analysis performed, the only risk that is identified for the device is inherent to its operation and does not vary either with the context or with the variation of the user. This consists in the direct exposure of the eyes to the light emitted by the device.

- The documentation accompanying the device takes this danger into account, and clearly defines it as misuse. All the implemented means of protection are not able to eliminate it completely, but the introduction of a positioning control system for the device, as explained in the User Manual, greatly limits the risk of involuntary eye exposure. Overall and on the basis of the analysis, evaluations and controls of the risks set out in the risk analysis document of the device, and of the analysis of the individual residual risks, the sum of the overall residual risk is considered ACCEPTABLE, considering the benefits brought by the testing and training method.
- Expected and foreseeable side effects: scientific literature reports that the use of blue light can lead to temporary and transient hyper-pigmentation in the peri-wound skin. In the cases described, this hyper-pigmentation disappears in a few tens of seconds. No direct observations from EMOLED have been found to date.
- Usage errors and abnormal uses: It is defined as "usage error", an action or non-action, which has a different result from that expected by the manufacturer or by the user of the medical device. It is defined as "abnormal use", an action or non-action by the user of a medical device, as a result of a behavior that goes beyond any possibility of risk control by the manufacturer.

Usage errors relating to medical devices that led to death or serious deterioration of the state of health or to a serious danger to public health must be reported by the manufacturer to the Ministry of Health when the manufacturer notices a significant change in the trend ( typically an increase in frequency) or a significant change in the way a problem presents itself that could potentially lead to death or serious deterioration in health or represent a danger to public health, or the manufacturer takes corrective action to prevent a death, a serious deterioration in health or a serious danger to public health. Abnormal use does not necessarily have to be reported by the manufacturer to the Ministry of Health according to the reporting procedures. Abnormal use should be managed by the health facility. If a manufacturer becomes aware of abnormal use cases, he can bring them to the attention of other appropriate organizations and health facility personnel.

#### ***Safety follow-up for subjects withdrawn from the study or who have completed the study***

Each morbid condition derived from each patient's incident will be monitored throughout the whole study period. The subjects that withdrew from the experimentation after the treatment with the device under study for any reason, will undergo a continued monitoring of the effects of the incident until the results from the tests related to the adverse event, and required by the SOC, will recover to baseline or until the investigator will determine that those events are not clinically relevant anymore.

All the subject who still present ongoing effects of an incident upon completion of the study will be monitored until the test results are not back to baseline, or is no longer expected from them to change, or until the investigator does not determine that those results are no longer clinically relevant.

### **Amendments to the clinical evaluation plan**

If, during the study, a modification to the protocol is deemed necessary the investigator communicates this need to the sponsor, who convenes the investigator of the coordinator centre, the study director and any other experts in the field, and discusses the proposed variations and, where appropriate, submits a request for amendment to the Ethics Committees to approve the changes deemed necessary.

If a substantive amendment request is necessary, the clinical trial will be suspended until approval has been received by the relevant ethics committees.

### **Early termination and suspension of clinical evaluation**

In the event of suspension or early termination of the study by the sponsor, taken as a safety measure due to events related to the conduct of the study that may affect the health of the patients recruited, the promoter is required to notify the Ministry of Health and the Ethics Committees involved within 90 days from the recruitment of the last patient or the early closure. In case of suspension or early termination of the study not for safety reasons, the sponsor shall justify and explain their decision. The suspended clinical trial cannot be reactivated unless a substantive amendment and the positive opinion of the Ministry of Health and the Ethics Committees have been submitted.

### **Statistics**

#### **Sample number**

Despite the presence in the scientific literature of data on average healing times of diabetic foot ulcers, the absence of clinical experience that associates blue light treatments with the therapy of this type of lesions and the lack of reliability of any inference based on clinical studies that associate this type of treatment with other types of skin lesions, due to the different etiologies and types of patients, it is not possible to perform a reliable calculation of the sample number.

The predefined sample size was therefore set on the basis of considerations concerning the recruitment capacity of the centre involved in the project. Based on an estimate of historical clinical activity data at the Diabetology Unit, where patients will be enlisted, the number of patients with diabetic foot ulcers is about 500 patients/year of which about 35% is affected by neuroischemic ulcer.

With an average of 30% of these patients reaching a healing rate of more than 50% in the first two weeks, and a further percentage of patients being excluded at the time of recruitment based on inclusion/exclusion criteria, in 18 months of enlistment it is possible to reach a number of 40 patients compared to a percentage of drop-out/denial equal to about 25%. A total of 40 patients will be recruited, 20 patients per arm.

Thus, this study is intended as a "proof of concept", the results of which may be used as preliminary information to define the sample size in later studies.

### **Management of missing data**

As a pilot study based on a limited number of patients, the study will also include patients who do not complete the study according to the principle of "intention to treat" and the resulting missing data will be processed through the imputation technique of the missing data last observation carried forward-LOFC.

In case the patient does not leave the study but skips one or more control visits, the averages of the two adjacent visits or the last available data (LOCF) will be taken into consideration.

### **Statistical analysis**

Demographic and clinical data will be presented in tables and graphs in the form of frequencies and percentages for categorical variables, mean, standard deviation, median and interquartile range for continuous variables, differentiating by reference population and treatment group.

In the first analysis a qualitative comparison between the treatment groups will be carried out (healed/not healed) through the test  $\chi^2$  or the exact test of Fisher in the case of counts of less than 5. The results will be presented in contingency tables and bar charts.

A quantitative comparative statistic between treatment groups will then be performed by comparing the percentage reduction in the area of injury, the variation in quality of life level (QoL) and the variation in pain perception (VASS) through Mann-Whitney's nonparametric test.

The choice to perform a non-parametric analysis lies in the low sample size and therefore it is preferred to have more conservative significance values. The results will be presented in tables with median and interquartile interval in the two groups with its p.value and graphically through the box plot.

To analyze the internal and time-related differences between groups, Friedman's non-parametric test for the outcome variables will be performed.

Generalized linear models (GLM) will be used to investigate whether differences between the two groups are influenced in a confusing way by demographic, clinical covariates, pre-treatment measurement, and to measure their impact which will allow us to understand which variables they include on the outcome and will also allow us to analyze the differences between the equal groups of these covariates.

For the comparison about recovery time, since the study is based on the principle of "intention to treat" and therefore there is no caesura, it will be performed by comparing the average recovery times through the non-parametric test of Mann-Whitney.

Then a descriptive statistic will be made through tables with frequencies and percentages, and bar charts of the treatment satisfaction indices in patients and operators. In addition, adverse events in both groups will be described, if present.

Due to the generally asymmetric nature of the cost distribution, the comparison of the costs associated with the two treatment arms, both from the perspective of the SSN and the Company, will be carried out using the non-parametric U test of Mann-Whitney.

Non-generalized linear regression models will be used to assess differences between groups, net of confounding factors.

The cost effectiveness of the two treatments in the time horizon of the study will be assessed by calculating the incremental cost effectiveness ratio (ICER) and expressed in terms of incremental cost for "quality adjusted life years" QALY.

Extrapolation of the results of the cost-effectiveness assessment by simulating longer time horizons will be carried out considering decision models (e.g. Markov models) and, where appropriate, integrating the data collected in the study with literature and/or evidence from other studies. All significance tests will have a statistically significant  $p < 0.05$  value. The analysis will be carried out with the open source software R Commander (v. 2-2.0).

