#### **Endpoints**

##### *Study primary endpoint*

The primary endpoint of the study will be the percentage of lesions considered healed (meaning as having a lasting and complete re-epithelialization) in the two groups at the twenty-fourth week of observation.

Healing must be confirmed by the Principal Investigator or their staff during an outpatient visit at the reference center participating in the study; the date of the recovery will in any case be indicated as the one of the first response, if it had occurred before the last visit to the reference center.

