Patients will be randomized into the two arms of the study according to a list of random numbers generated by special IT tools and communicated by the scientific supervisor to the Care Provider via e-mail.

It is a 1: 1, single-block randomization of 40 patients distributed in the two groups (treated and control). After the two-week enrollment observation period, the Investigator at the outpatient center will ascertains the conditions for the study prosecution and he will notify the Head of the Care Providers to take charge of the patient included in the study and to proceed with the assignment to one of the groups. In this way, the Investigator at the outpatient center will be blinded to the treatment performed at home by the patient.

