#### *Inclusion Criteria:*

- *Patients suffering from neuro-ischemic diabetic foot ulcer grade IC or IIC according to the University of Texas Wound Classification (22); If the patient has two or more lesions, which may fall within the inclusion criteria, the most serious lesion (index lesion) will be selected and followed for the entire duration of the study;*
- *Patients who, following hospital discharge or after the first outpatient assessments, are followed by Home Care Nursing Service and are always monitored at the same referral center;*
- *Patients with type I or II diabetes, with glycated haemoglobin≤ 10%;*
- *Patients willing to constantly wear the offload devices prescribed by the reference center;*
- *Patients with ulcer localized on toes, on the plantar side, on the margins or on the dorsum of the foot wider than 1 sqcm;*
- *Patients with peripheral neuropathy confirmed with Monofilament (Semmes-Weinstein 5.07 / 10g);*
- *Patients with ABPI of 0.7 - 0.9, ankle PA> 70mmHg, TcPO2 between 36 - 50 mmHg;*
- *Patients with lesions lasting from 1-24 months;*
- *Patients who understand the purpose of the Clinical Study and provide their informed consent in writing.*

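### The primary comparison of healing at week 24 is valid but leaves out baseline lesion area, which the trial already measures; adjusting for that one covariate would add some power at no data cost

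*Protocol*

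**What the plan says.** Under *Study primary endpoint* the Protocol states: "The primary endpoint of the study will be the percentage of lesions considered healed" in each group at week 24. Under *Statistical analysis* the matching test is set out: "a qualitative comparison between the treatment groups will be carried out (healed/not healed", by chi-square, "or the exact test of Fisher in the case of counts of less than 5". No covariate enters this comparison.

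Later in the same section, generalised linear models (GLMs) are to examine whether group differences are "influenced in a confusing way by demographic, clinical covariates, pre-treatment measurement". They are also meant to show which variables act on the outcome, and they "will also allow us to analyze the differences between the equal groups of these covariates". The text gives no number of covariates, does not tie the models to one outcome, and does not call them a primary analysis. A further sentence, "Non-generalized linear regression models will be used to assess differences between groups, net of confounding factors", comes directly after the cost comparison and does not describe a model for a binary outcome.

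On lesion size, the *Inclusion Criteria* end the list of ulcer sites with "on the margins or on the dorsum of the foot wider than 1 sqcm", which is a lower limit with no upper one. *Measurable parameters* and *Image acquisition* provide for photographs from the first visit and for calculation of the wound area. *Study design* describes a "single-block randomization of 40 patients" and names no stratification factor.

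**The concern.** Complete closure within a fixed 24 weeks plausibly depends on how large the lesion was at the start. With 20 patients per arm and size open-ended at entry, area may explain a useful share of the variation in healing. A test that leaves it out gives up precision that costs nothing to recover, and a reader faced with a chance difference in size between arms has no named analysis to turn to.

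The GLM is the one place in the plan where healing could be adjusted, but it is framed as a check on confounding over three open classes of covariates. In 40 patients the number of covariates matters. The Protocol, under *Sample number*, offers the results as preliminary information for sizing later studies, so an overstated odds ratio from a crowded model could be carried forward.

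**Working it through.** **Inputs from the Protocol.** 40 patients, 20 per arm; binary healing at week 24; significance at p < 0.05 (two-sided assumed); intention to treat with carried-forward values, so all 40 stay in the table. The number 40 is a recruitment figure. No power, effect size or healing rate is given, so there is no stated power to reproduce.

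**Assumed inputs.** About 50% healed overall; z = standardised log baseline area; logit P(healed) = β(arm − 0.5) + g·z, with g about 0.5, 1.0 or 1.5 per SD and β = 1.1 or 2.0. At β = 2.0 the healing rates are about 28–33% v 67–72%, a large effect.

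**1. The planned test.** By exact enumeration, the chi-square/Fisher rule has size 3.5–3.8% at common healing rates of 40–50%. Its power is 21% for 40% v 60% and 44% for 40% v 70%. It is valid and slightly conservative.

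**2. Power from adjusting for area alone (simulation).**

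| Slope g per SD | β = 1.1: chi-square | β = 1.1: adjusted | Gain | β = 2.0: chi-square | β = 2.0: adjusted | Gain |
|---|---|---|---|---|---|---|
| 0.5 (0.6 for β = 1.1) | 33% | 36% | 3 | 80% | 84% | 4 |
| 1.0 | 27% | 32% | 5 | 70% | 78% | 8 |
| 1.5 | 21% | 27% | 6 | 56% | 72% | 16 |

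The β = 1.1 columns use the Wald test from a one-covariate logistic model. The β = 2.0 columns use a re-randomisation test on residuals of a baseline-only logistic fit. Repeat runs at β = 2.0 gave gains of 2/7/15 points and of 3 to 16 points. The re-randomisation test at β = 1.1 gave 33/26/21% rising to 36/33/29%, gains of 3/7/8, so the choice of adjusted test moves the upper end by about two points. The size of the adjusted test was 4.5–5.5%. Fisher's test used throughout would have 70/58/44% at β = 2.0, but part of that shortfall is Fisher's conservatism and not the missing covariate.

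**3. Precision.** At β = 1.1 the SD of the risk difference falls from 0.152 to 0.148, from 0.152 to 0.141 and from 0.153 to 0.131, which is 3%, 7% and 14%.

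**4. Chance imbalance.** The difference in mean z between arms has SD √(2/20) = 0.316. P(|difference| ≥ 0.4) = 2·P(Z > 0.4/0.316) = 2·P(Z > 1.265) = 0.21.

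**5. The GLM, if fitted to healing.** The smaller of healed and not healed is at most 20 in 40 patients: 40 × 0.5 = 20, 40 × 0.4 = 16, 40 × 0.3 = 12. For a true log odds ratio of 1.2 (OR e^1.2 = 3.3), slope 1.0 and only the first covariate prognostic:

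| Covariates | Median log OR | Median OR |
|---|---|---|
| 3 (one per named class) | 1.35 | 3.9 |
| 5 | 1.47 | 4.3 |
| 7 | 1.65 | 5.2 |
| 9 | 1.78 | 5.9 |

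Under no effect the mean log odds ratio stays near 0 (−0.02 to 0.02). With 5 to 9 covariates the type I error is 8–12% for the likelihood-ratio test but about 5.5% for the Wald test.

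**The case against.** The strongest reply is that nothing here is wrong. An unadjusted test of a randomised binary outcome is valid, and its error rate already allows for chance imbalance, so the 21% figure shows no bias. The Protocol also lists a pre-treatment measurement among the GLM covariates, so some baseline adjustment is foreseen. The covariate list is something a protocol commonly leaves to the SAP. The study calls itself a pilot, the strength of area as a predictor is assumed, and the largest power gain needs both a large effect and the steepest slope. All of this stands, and it limits the point to an improvement.

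Three stronger readings are tempting, and the Protocol does not support them.

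- *The named covariate classes already overfit the data.* No number of covariates is stated. One per class gives a median of 1.35 for a true 1.2, which is mild; clear inflation needs five or more.
- *The GLM would produce false positives.* There is no bias under the null, and the excess appears only with the likelihood-ratio test. The Protocol does not say which test it would use.
- *The trial will report two rival answers for its primary endpoint.* The chi-square/Fisher comparison comes first and matches the endpoint, while the GLM is described as a check on confounding. It does include a comparison of arms at equal covariates, but it is not offered as a competing primary analysis.

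What the reply leaves standing is that the comparison the Protocol itself fixes for its primary endpoint omits a measured, plausibly prognostic covariate. The adjustment that is foreseen serves another purpose and has no limit.

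**Conclusion.** The point holds as a modest, inexpensive improvement. The primary test is valid but less efficient than it could be. Adjusting for log baseline area gains about 3 to 6 points of power at a conditional log odds ratio of 1.1 and about 3 to 16 points at 2.0, with size near 5%. These gains rest on an assumed healing rate of about 50% and assumed slopes of roughly 0.5 to 1.5 per SD. If area predicted healing only weakly, the gain would be at or below the lower end.

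The warning about the GLM is conditional. If it is fitted to healing with five or more covariates in 40 patients, a non-null odds ratio is overstated, at a median log odds ratio of about 1.5 to 1.8 for a true 1.2. The practical risk is an exaggerated effect passed into the sizing of a later study, not a spurious finding.

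**What to change.** In *Statistical analysis*:

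- Name one adjusted analysis of the primary endpoint: healed at week 24 on arm plus log lesion area at randomisation, that is, at the end of the two-week run-in. Report the standardised risk difference with its confidence interval. A risk difference can be set directly beside the unadjusted one. An odds ratio cannot, because it changes on adjustment even without imbalance.
- Keep chi-square/Fisher as the unadjusted companion and say which of the two analyses leads.
- Limit any further GLM for healing to one or two baseline covariates named in advance, and label any search for influential variables as exploratory.

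A re-randomisation test on residuals of the baseline-only model is one way to hold the size at 5%; it is an option, not a requirement.

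The cost is protocol wording and a few lines of R, with no new data or patients. The small downside is that the adjusted estimate depends on a simple one-covariate model, which is why the unadjusted result stays beside it.

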#### *Study secondary endpoints*

1. Healing time (in which healing is represented by a lasting and complete re-epithelialization);
2. Reduction of the lesion surface in both arms, during the 20 weeks, measured in absolute terms (square centimeters) and as % of the initial size;
3. Quality of life (QoL), evaluated both with specific questionnaires (EuroQoL-5D) and generic questionnaires (Wound-QoL);
4. Perception of pain measured with a subjective analogue rating scale (VAS);
5. Assessment of the costs related to the two arms in the perspective of the National Health System, NHS (considering only direct health costs) and in the perspective of the Society (considering beyond direct health costs, direct non-health costs and indirect costs);
6. Patient's satisfaction with the EmoLED therapy, assessed by administering specific questionnaires;
7. Appreciation, complexity and usefulness of the EmoLED therapy by the operators assessed through the administration of specific questionnaires;
8. Security of treatment (number of Adverse Events in the two groups);
9. Evaluation of the cost-effectiveness of using EmoLED for the treatment of ulcers.

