### **Measurable parameters**

Following enrollment and signature of the informed consent, during the first visit / treatment, at the reference outpatient center, the salient data and photographic images of the lesion of each patient will be collected in the appropriate data collection form (see Annex).

During the home visits, twice a week (concomitantly with the dressing change and with the treatment with EmoLED for the Treated Group, respectively), photographic images of the lesion of each patient, some clinical data and the perception of pain through VAS scale will be collected. These variables will be measured at each

visit or until healing. During the visits (to be scheduled at least once every 30 days) carried out at the reference center participating in the trial, the clinical data on the Data Collection Form (see Annex), the photographic images of the lesion of each patient, pain perception using the VAS scale and quality of life data will be collected.

Questionnaires relating to the Quality of Life Section will be administered at the first visit and at the last visit. In particular, standard tools such as the generic questionnaire EQ-5D and the specific questionnaire Wound-QoL will be administered, both available and validated in Italian.

The parameters used that will be found for the definition of the result in the study are:

- Re-epithelialization of the lesion / reduction of the lesion area through data collection form and photographic images of the lesions treated with EmoLED and control lesions (Annexes B, C);
- Intensity of pain perceived by the patient through the VAS scale (Annexes B, C);
- presence of infection (Annexes B, C);
- Level of quality of life perceived by the patient through a questionnaire on the quality of life (EuroQoL and Wound-QoL) (Annexes D, E);
- Appreciation of the therapy (patient) through a specific questionnaire to be filled in by the patient (Annex F);
- Satisfaction, complexity and usefulness of using the device (operator) through a specific questionnaire to be filled in by the operator (Annex G);
- Direct and indirect costs (Annexes H, I);
- Detection of Adverse Events (Annexes B, C).

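### For quality of life and pain, the reported comparison is an unadjusted Mann-Whitney test on change; the baseline-adjusted comparison should lead, with its covariate fixed

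*Protocol*

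**What the plan says.** Quality of life (EQ-5D and Wound-QoL) and pain on a VAS are secondary endpoints (Protocol, Study secondary endpoints). Baseline values are planned for both. On quality of life, Measurable parameters states: "Questionnaires relating to the Quality of Life Section will be administered at the first visit and at the last visit". Pain is recorded at each visit (Registration of clinical data).

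Statistical analysis makes the between-arm comparison by "comparing the percentage reduction in the area of injury, the variation in quality of life level (QoL) and the variation in pain perception", with a Mann-Whitney test. Results are to be tabled as medians and interquartile intervals per group with that test's p-value. No covariate enters. The reason given is: "The choice to perform a non-parametric analysis lies in the low sample size and therefore it is preferred to have more conservative significance values".

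The section then adds generalized linear models, to see whether group differences are "influenced in a confusing way by demographic, clinical covariates, pre-treatment measurement, and to measure their impact". It says that the models "will also allow us to analyze the differences between the equal groups of these covariates", which in context means the group difference at equal covariate values. It does not say which outcomes the models cover, which covariates enter, or which analysis decides if the two disagree.

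The sample size is 40, 20 per arm, set by recruitment capacity. The results are meant to inform the sample size of later studies (Statistics, Sample number).

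**The concern.** A change score subtracts the baseline in full, whatever its actual relation to the outcome. Unless that correlation is close to 1, this adds baseline noise to the comparison. Adjusting for baseline subtracts only the part that predicts the outcome, so it is more precise whenever the correlation is below 1. With 20 patients per arm the difference can matter.

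The tabled medians and p-values for quality of life and pain would come from the less precise of the two analyses that the plan names. The more precise one is framed mainly as a check on confounding and, with an open covariate list, is not a prespecified estimate.

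The point estimate is also affected. A chance baseline difference between arms carries into the change-score difference, in a trial whose results may be used to plan the next one.

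**Working it through.** **Inputs from the protocol.** 20 patients per arm, 1:1; significance level 0.05; Mann-Whitney on change. No power, effect size, SD or correlation is stated, so there is no stated power to reproduce.

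**Assumptions.** Two-sided test (sidedness is not stated); bivariate normal baseline and outcome with equal SDs; true difference 0.8 SD; baseline-outcome correlation ρ from 0.3 to 0.8.

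**Variance.** Per patient, in units of SD²:
- change score: 2(1 − ρ)
- baseline-adjusted outcome: 1 − ρ²
- ratio, adjusted to change: (1 − ρ²) / [2(1 − ρ)] = (1 + ρ)/2, that is 0.65, 0.75, 0.85 and 0.90 at ρ = 0.3, 0.5, 0.7 and 0.8.

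Under normality the Mann-Whitney test has a further relative efficiency of 3/π = 0.955.

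**Difference detectable with 80% power (normal approximation).** The base factor is (1.960 + 0.842) × √(2/20) = 0.886. Multiply by √[2(1 − ρ)/0.955] for Mann-Whitney on change and by √(1 − ρ²) for ANCOVA:

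| ρ | Mann-Whitney on change | ANCOVA |
|---|---|---|
| 0.3 | 1.07 SD | 0.85 SD |
| 0.5 | 0.91 SD | 0.77 SD |
| 0.7 | 0.70 SD | 0.63 SD |
| 0.8 | 0.57 SD | 0.53 SD |

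**Simulated power, 20 per arm, 0.8 SD (3,000 runs per setting).**

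| ρ | Mann-Whitney on change | ANCOVA | Rank ANCOVA | Deficit v ANCOVA | Deficit v rank ANCOVA |
|---|---|---|---|---|---|
| 0.3 | 53% | 73% | 70% | 20 | 17 |
| 0.5 | 66% | 79% | 75% | 13 | 9 |
| 0.7 | 87% | 92% | 89% | 5 | 2 |

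A separate simulation of 6,000 runs gave 52 v 72%, 67 v 80% and 87 v 93% for Mann-Whitney against ANCOVA, and 96 v 98% at ρ = 0.8. If 25% of patients were lost after randomisation (20 × 0.75 = 15 per arm), it gave 39 v 58%, 52 v 66% and 75 v 83% at ρ = 0.3, 0.5 and 0.7.

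**Type I error.** With no true effect and ρ = 0.5, 6,000 runs gave 4.8% for Mann-Whitney on change and 5.2% for ANCOVA. The simulation standard error is √(0.05 × 0.95/6000) = 0.3 points, so neither differs from 5%. The conservatism given as the reason for the rank test brings no extra protection here.

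**Chance imbalance.** The baseline difference between arms has standard error √(2/20) = 0.316 SD. A difference above 0.4 SD in either direction therefore has probability 2[1 − Φ(0.4/0.316)], about 21%. With no treatment effect, a 0.4 SD imbalance shifts the difference in mean change by (1 − ρ) × 0.4 = 0.2 SD at ρ = 0.5. Baseline adjustment removes that shift.

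**The case against.** The strongest reply is that baseline adjustment is already planned. The models include the pre-treatment measurement and are meant to give the group difference at equal covariate values. A reader might infer from the Mann-Whitney sentence alone that the baseline data are discarded; the same section shows that they are not. This part of the reply stands. What remains is narrower: which analysis leads, and which covariate it uses. A statistical analysis plan could settle both, but the protocol itself already names the test and the table that carry the result.

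A reader might also extend the point to lesion area, which the same sentence covers. The documents do not support that. Area is compared as percentage reduction, so it is already scaled to baseline, and the variance ratio above, derived for absolute differences, does not apply. Nor do ties help the argument: healed ulcers tie at 100% reduction, but they would equally tie at zero cm² in an adjusted analysis of final area. In illustrative simulations, rank ANCOVA of final area ranged from about 4 points worse to 5 points better than Mann-Whitney on percentage reduction, depending on the assumptions. Not even the direction of the gain is settled.

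The reply is also right that the loss for quality of life and pain depends on undocumented inputs. It is only about 1.5 points against ANCOVA at ρ = 0.8. VAS and questionnaire scores may not be normal, although the rank version addresses much of that.

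Finally, a rank test on change is valid. The small-sample rationale is a reason to prefer a rank method, but not to leave the baseline out of it.

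**Conclusion.** The point holds for quality of life and pain only, as a matter of efficiency and not of validity. The plan leads with the less precise of its two analyses and leaves the better one without precedence or a fixed covariate. Under the stated assumptions the cost is about 20, 13 and 5 power points against ANCOVA, and 17, 9 and 2 against rank ANCOVA, at correlations of 0.3, 0.5 and 0.7, with no gain in type I error control. Since the protocol gives no correlation, SD or effect size, these figures show a range and do not estimate this trial's loss.

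It would be too strong to conclude that the trial misses its power: none is claimed, and 40 patients is a recruitment figure. This is a minor improvement to secondary endpoints of a proof-of-concept study.

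**What to change.** In Statistical analysis, for quality of life and pain:
- Name the baseline-adjusted comparison as the main analysis: ANCOVA of the final value on treatment arm, with the baseline value of the same measure as the single prespecified covariate. Use rank ANCOVA if a non-parametric method is to be kept.
- State which visit supplies the baseline value.
- Report the adjusted difference with a confidence interval. If rank ANCOVA gives the p-value, show the ANCOVA difference and interval beside it, because the rank test gives no difference in scale units.
- Keep Mann-Whitney on change as a sensitivity analysis, and label models with further covariates as exploratory.

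Leave the area comparison as it is on this ground. The cost is a change of wording: no new data, visits or patients. The downside is one extra model assumption, a common linear relation of outcome to baseline, which the rank version relaxes.
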